16. SAFETY OUTCOMES

All outputs for safety outcomes will be based on the Safety Analysis Set.

There will be no statistical tests performed for differences between the treatment groups with regards to safety data.

16.1. ADVERSE EVENTS

Adverse Events (AEs) will be coded using MedDRA central coding dictionary, Version 19.1.

Treatment-emergent AEs are defined as AEs that first occurred or worsened in severity after the first administration of the IMP. Any AEs started after the informed consent form has been signed and before the first administration of the IMP will be considered as Non-TEAEs.

The relationship to study drug will be summarized as related and unrelated. AEs that are recorded as 'related', 'possibly' or 'probable' in the eCRF are categorized as 'related' whereas the AEs that are recorded as 'unrelated' and 'unlikely' are categorized as 'unrelated'. Missing relationship/missing severity would be considered by the worst case as "Related" and "Grade 5" respectively.

Listings will include TEAEs and Non-TEAEs. Separate listing will be provided for AEs leading to discontinuation, serious adverse events (SAEs) and deaths.

For each treatment group, TEAEs, non-TEAEs, drug related AEs, relationship to study drug, AEs leading to discontinuation and SAEs will be summarized by primary SOC and PT. Also, summary of National Cancer Institute Common Terminology Criteria for Adverse Events (NCI-CTCAE, version 4.03) will be presented by primary SOC and PT. AE tables include number and percentage of subjects and number of events.

An overall summary of adverse events will be produced including frequency counts of:

- number of subjects with at least one TEAE
- number of subjects with at least one non-TEAE
- number of subjects with at least one serious TEAE
- number of subjects withdrawn from treatment with at least one serious TEAE

Document:

CCI

Author:

PPD

Version Number:

1.0

Version Date:

06 Oct 2017

Template No: CCI

Reference: CCI

Effective Date: 01Apr2016

Copyright © 2009, 2010, 2012, 2016 Quintiles Transnational Corp. All rights reserved.

The contents of this document are confidential and proprietary to Quintiles Transnational Corp. Unauthorized use, disclosure or reproduction is strictly prohibited.

- number of subjects with at least one related serious TEAE
- number of subjects who discontinue from the study due to a TEAE
- number of subjects with at least one TEAE with CTCAE severity grade ≥ 3
- number of subjects with at least one related TEAE
- number of deaths

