8.1.1 Adverse Events

The Investigator is responsible for recording all AEs observed during the study from the time the patient signs the ICF until the last contact of the patient.

Definition of AE: An AE is any untoward medical occurrence in a clinical study patient whether or not a pharmaceutical product is administered and which does not necessarily have a causal relationship with this treatment. An AE can therefore be any unfavorable and unintended sign (including an abnormal laboratory finding), symptom, or disease temporally associated with the use of a medicinal product or IMP, whether or not considered related to the medicinal product or IMP.

An AE can also be a new disease or exacerbation of an existing disease (a worsening in the character, frequency, or severity of a known condition).

Abnormal laboratory values, or test results, physical examination findings, and other abnormal investigational findings (i.e., ECG) should not be reported as AEs unless they are associated with clinical signs and symptoms that are considered clinically significant, require therapy (e.g., hematologic abnormality that requires transfusion or hematological stem cell support), or lead to treatment discontinuation.

Death is not considered an AE but an outcome.

Disease progression can be considered as a worsening of a patient's condition attributable to the disease for which the IMP is being studied. It may be an increase in the severity of the disease under study and/or increase in the symptoms of the disease and should be considered as disease progression and not an AE.

Adverse Drug Reaction (ADR): Any untoward and unintended response in a subject to an IMP which is related to any dose administered to that subject.

Definition of Serious AE (SAE): An SAE, experience or reaction, is any untoward medical occurrence (whether considered to be related to IMP or not) that at any dose:

- Results in death;
- Is life-threatening (the patient is at a risk of death at the time of the event; it does not refer to an event which hypothetically might have caused death if it were more severe);

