10.4.1 Primary Endpoint Analyses

10.4.1.1 Adverse Events

Treatment-emergent AEs are defined as AEs that first occurred or worsened in severity after the first administration of the IMP.

Summaries over SOC, PT and listings of AEs leading to death, SAEs, AEs, and AEs that led to discontinuation of study treatment will be presented. Summaries will also be presented by relationship to IMP and severity of the AE.

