6.3. BASELINE

Unless otherwise specified, baseline is defined as the last non-missing measurement (including unscheduled assessments) taken prior to the reference start date and/or time. If the last non-missing measurement is recorded on the day of IP administration and is specified to be done pre-dose as per the protocol then it will be considered baseline. For Adverse Events/Concomitant Medications if start date and/or time of measurement and IP administration coincide, that measurement will be considered as post-baseline.

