APPENDIX 1. PARTIAL DATE CONVENTIONS

Imputed dates will NOT be presented in the listings.

Algorithm for Treatment Emergence of Adverse Events:

START DATE	STOP DATE	ACTION
Known	Known	If start date and time < study med start date and time, then not TEAE If start date and time >= study med start date and time, then TEAE
	Partial	If start date and time < study med start date and time, then not TEAE If start date and time >= study med start date and time, then TEAE
	Missing	If start date and time < study med start date and time, then not TEAE If start date and time >= study med start date and time, then TEAE
Partial, but known components show that it cannot be on or after study med start date and time	Known	Not TEAE
	Partial	Not TEAE
	Missing	Not TEAE
Partial, could be on or after study med start date and time	Known	If stop date and time < study med start date and time, then not TEAE If stop date and time >= study med start date and time, then TEAE
	Partial	Impute stop date and time as latest possible date and time (i.e. last day of month if day unknown or 31st December if day and month are unknown), then: If stop date and time < study med start date and time,

Document:

CCI

Author:

PPD

Version Number:

1.0

Version Date:

06 Oct 2017

Template No: CCI

Reference: CCI

Effective Date: 01Apr2016

Copyright © 2009, 2010, 2012, 2016 Quintiles Transnational Corp. All rights reserved.

The contents of this document are confidential and proprietary to Quintiles Transnational Corp. Unauthorized use, disclosure or reproduction is strictly prohibited.

START DATE	STOP DATE	ACTION
		then not TEAE If stop date and time >= study med start date and time, then TEAE
	Missing	Assumed TEAE
Missing	Known	If stop date and time < study med start date and time, then not TEAE If stop date and time >= study med start date and time, then TEAE
	Partial	Impute stop date and time as latest possible date and time (i.e. last day of month if day unknown or 31st December if day and month are unknown), then: If stop date and time < study med start date and time, then not TEAE If stop date and time >= study med start date and time, then TEAE
	Missing	Assumed TEAE

Document:
Author:

CCI
PPD

Version Number:
Version Date:

1.0
06 Oct 2017

Template No:
Effective Date: 01Apr2016

Reference: CCI

Algorithm for Prior / Concomitant Medications:

START DATE	STOP DATE	ACTION

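### SAP 16.1 and Appendix 1 class any adverse event with pre-dose onset as not treatment-emergent on dates alone, although the definition they serve also counts post-dose worsening

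*SAP*

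**What the plan says.** The protocol's analysis section gives the definition: "Treatment-emergent AEs are defined as AEs that first occurred or worsened in severity after the first administration of the IMP" (Protocol 10.4.1.1). SAP 16.1 repeats it, covering "AEs that first occurred or worsened in severity after the first administration of the IMP". The sentence that follows in SAP 16.1 is unconditional: "Any AEs started after the informed consent form has been signed and before the first administration of the IMP will be considered as Non-TEAEs".

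SAP Appendix 1 turns this into an algorithm for treatment emergence. Although the appendix is titled as a set of partial-date conventions, the algorithm also covers fully known dates. For a known start date its rule is "If start date and time < study med start date and time, then not TEAE", whatever the stop date. For a start date described as "Partial, but known components show that it cannot be on or after study med start date and time", the result is not TEAE in all three stop-date rows.

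SAP 3.3 names one change from the protocol's analysis, the specification of the repeated-measures efficacy model. It does not mention the TEAE definition.

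**The concern.** Adverse event incidence and severity are part of the primary endpoint (Protocol 4.1), and the SAP gives two answers for the same event. Because Appendix 1 is the rule a programmer would code, the date-only answer is the likelier one to reach the tables. The part of the definition about worsening would then never apply to a record with pre-dose onset.

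This also runs against the caution the SAP shows elsewhere. A missing severity is counted as Grade 5, a missing relationship as related, and an event with neither start nor stop date is assumed to be a TEAE. Under the present wording an event with no dates at all counts as treatment-emergent, while one with a documented post-dose worsening may not.

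**Working it through.** No planned figure is at issue, so the check compares the rules on one event and counts what depends on them.

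**Test case.** An event starts during screening at Grade 1, rises to Grade 3 after the first infusion, and is kept on one record with its original onset date.

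| Rule | Result |
|---|---|
| Definition (Protocol 10.4.1.1; SAP 16.1, definition sentence) | TEAE, because severity worsened after first dose |
| SAP 16.1, next sentence | Non-TEAE, because onset was between consent and first dose |
| SAP Appendix 1, known start date | Not TEAE, because start precedes study medication |

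**Appendix 1, row by row.** Four start-date classes × three stop-date classes = 12 rows. None uses severity.

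| Start date | Stop date | Rows | Treatment of a pre-dose onset that continues after dosing |
|---|---|---|---|
| Known | any | 3 | Not TEAE |
| Partial, must be pre-dose | any | 3 | Not TEAE |
| Partial (could be post-dose) or missing | known or partial | 4 | Not TEAE only if the (imputed) stop precedes dosing |
| Partial (could be post-dose) or missing | missing | 2 | Assumed TEAE |

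3 + 3 + 4 + 2 = 12. The conflict sits in the first six rows. The other six do not exclude an event that continues after dosing.

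**Outputs that depend on the classification.** SAP 16.1 plans a TEAE table by system organ class and preferred term, and an overall summary of nine lines. Two of those lines (non-TEAEs and deaths) are not limited to TEAEs, so 9 − 2 = 7 are. The test event drops out of the TEAE table and out of whichever of the seven lines it would have met. It stays in the listings, which cover TEAEs and non-TEAEs, and in the non-TEAE table.

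**Size.** Protocol 10.1 plans 12 patients per arm. One affected patient changes a line for that arm by at most 1/12 = 8.3 percentage points. The change is 0 if the patient has another event that qualifies for the same line.

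**Window.** An affected event can start only between consent and first dose. Protocol Table 1 (footnote a) limits screening to 15 days before the first infusion. The documents give no event rate for that period, so no expected number of affected events can be stated.

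**The case against.** The strongest defence is that the gap may never arise in the data. Protocol 8.1.1 says an adverse event can be an exacerbation, including "a worsening in the character, frequency, or severity of a known condition", and Protocol 8.1.1.1 asks for each event to be recorded separately. If sites open a new record with its own onset date at each worsening, the date algorithm gives the right answer. This stands as a mitigation but does not close the gap. The protocol allows the practice without requiring it, and the data items named in 8.1.1.1 include severity but no date of grade change. The eCRF completion instructions mentioned in Protocol 9.4 might settle it, but they are not among the documents and the SAP cites no such convention.

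The scope is also narrow, and this stands. Significant findings present at Screening go to the medical history or current conditions page (Protocol 8.1.5). If a later worsening of such a condition is entered as an adverse event, it has a post-dose onset and is classed correctly. Worsening of myasthenia gravis itself is treated as disease progression, not an adverse event (Protocol 8.1.1). What remains is a new event that starts in screening, is ongoing at first dose, rises in grade afterwards and stays on one record. Safety data are not tested between arms (SAP 16), so no test result depends on it.

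Three stronger readings might be inferred, and the documents do not support them:

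- **That the event disappears from safety reporting.** It does not; it is listed and appears in the non-TEAE table.
- **That the other tables by system organ class and preferred term are known to keep it, or known to lose it.** SAP 16.1 says only that "drug related AEs, relationship to study drug, AEs leading to discontinuation and SAEs will be summarized by primary SOC and PT". It does not say whether those tables are limited to TEAEs, and the mock shells that would show this are not provided.
- **That SAP 6.3 confirms the date-only rule.** Its wording, "if start date and/or time of measurement and IP administration coincide, that measurement will be considered as post-baseline", resolves ties only. It says nothing about an event that began earlier and later worsened.

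**Conclusion.** The contradiction is real and can be read directly from the text. The definition counts post-dose worsening; the next sentence of SAP 16.1 and six of the 12 Appendix 1 rows exclude any event with pre-dose onset without looking at severity; and SAP 3.3 does not declare the departure.

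Its effect on results is probably small. The 8.3-point ceiling assumes 12 patients per arm in the safety set, a worsening kept on the original record, and no other event in that patient that qualifies for the line. The effect is nil if a worsening opens a new record. Nothing in the documents suggests that the overall safety conclusion would change. The point should still be settled before database lock, because it concerns the primary safety classification and costs little to correct.

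**What to change.** 1. In SAP 16.1, limit the non-TEAE sentence to events with onset between consent and first administration that did not worsen in severity on or after first administration.
2. In Appendix 1, make the six rows with known or certain pre-dose onset subject to the same exception. The other six rows can stay.
3. State in the SAP how worsening is identified. If a worsening opens a new adverse event record with its own onset date, stating that convention is enough and the row edits in step 2 are not needed.
4. If grades are kept on one record without dates, review events ongoing at first dose while still blinded and before lock, with site queries where the timing of a worsening is unclear. The blinded data review in Protocol 10.2 is a convenient occasion, although it is planned there for decisions on analysis sets.

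The cost is one clause, one condition in up to six rows and a few lines of code. If grades are undated, add a small amount of query work, since the database alone would not show when an event worsened. The change restores the protocol's own definition, so no protocol amendment is needed.

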Each AE is to be evaluated for duration, severity, seriousness and causal relationship to the IMP or study procedures. The action taken with the investigational drug and the outcome of the event must also be recorded.

Overdose

For the purposes of this study, exceeding the dosage requirements specified in this protocol represents an overdose. In case of suspected overdose, the patient should be treated according to standard medical practice based on the Investigator's judgment.

Severity

All AEs observed will be graded using the National Cancer Institute (NCI) Common Terminology Criteria for Adverse Events (CTCAE) version 4.03. The NCI CTCAE is a descriptive terminology which can be utilized for AE reporting. A grading (severity) scale is provided for each AE term. Grade refers to the severity of the AE. If a particular AE's severity is not specifically graded by the guidance document, the Investigator is to use the general NCI-CTCAE definitions of Grade 1 through Grade 5 following his or her best medical judgment. The CTCAE displays Grades 1 through 5 with unique clinical descriptions of severity for each AE based on the following general guideline:

- Grade 1: Mild; asymptomatic or mild symptoms; clinical or diagnostic observations only; intervention not indicated.
- Grade 2: Moderate; minimal, local or non-invasive intervention indicated; limiting age-appropriate instrumental activities of daily living (ADL).

- Grade 3: Severe or medically significant but not immediately life-threatening; hospitalization or prolongation of hospitalization indicated; disabling; limiting self-care activities of daily living (ADL).
- Grade 4: Life-threatening consequences; urgent intervention indicated.
- Grade 5: Death related to AE.

Relationship

The causal relationship between the IMP/study procedures and the AE has to be characterized as unrelated, unlikely, related, possible, and probable.

- Events can be classified as “unrelated” if there is not a reasonable possibility that the IMP caused the AE.
- An “unlikely” relationship suggests that only a remote connection exists between the IMP and the reported AE. Other conditions, including chronic illness, progression or expression of the disease state, or reaction to concomitant medication, appear to explain the reported AE.

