8.1.1.1 Reporting of Adverse Events and Serious Adverse Events

All AEs, that occur during the study from signature of informed consent until EoS (Visit 16), are to be recorded on the appropriate AE pages (either ‘serious’ or ‘non-serious’) in the

eCRF. The Investigator should complete all the details requested, including dates of onset, stop date (when applicable), severity, action taken, outcome, and relationship to IMP, and to study procedures. Each event should be recorded separately in the eCRF.

All AEs spontaneously reported by the patient or reported in response to the open question from the study personnel: 'Have you had any health problems since the previous visit/you were last asked?', or revealed by observation will be collected and recorded in the eCRF. When collecting AEs, the recording of diagnoses is preferred (when possible) to recording a list of signs and symptoms. However, if a diagnosis is known and there are other signs or symptoms that are not generally part of the diagnosis, the diagnosis and each sign or symptom will be recorded separately.

Any SAE, including death due to any cause, which occurs during this study after signature of informed consent, whether or not related to the IMP, must be reported immediately (within 24 hours of the study site's knowledge of the event). All SAEs will be recorded (within 24 hours) on the electronic SAE report form and the AE form in the eCRF, the Investigator or delegated site staff should check that all entered data is consistent. An alert email for the SAE report will then be automatically sent by email to the Sponsor's designated CRO (Quintiles) safety mailbox via the electronic data capture (EDC) system. In case the EDC system is not functioning correctly or the system is down, all SAEs should be reported by fax/email to Sponsor's designated CRO (Quintiles) using the SAE paper report form.

The report will contain as much available information concerning the SAE to enable the Sponsor (or an authorized representative) to file a report, which satisfies regulatory reporting requirements. These timelines apply to initial reports of SAEs and to all follow-up reports.

Criteria for documenting the relationship to IMP as well as severity, outcome, and action taken will be the same as those previously described.

All SAEs that are spontaneously reported within 30 days of a patient's last visit are to be collected and reported as previously described.

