9.3 Monitoring

The Sponsor has engaged the services of a CRO, named Quintiles, to perform all monitoring functions within this clinical study. Sponsor's designated CRO (Quintiles') monitors will work in accordance with Quintiles' standard operating procedures (SOPs) and have the same rights and responsibilities as monitors from the Sponsor organization. Monitors will establish and maintain regular contact between the Investigator and the Sponsor.

Monitors will evaluate the competence of each study site, informing the Sponsor about any problems relating to facilities, technical equipment, or medical staff. During the study, monitors will check that written informed consent has been obtained from all patients correctly prior to any study related procedures performed and that data are recorded correctly and completely. Monitors are also entitled to compare entries in eCRFs with corresponding source data and to inform the Investigator of any errors or omissions. Monitors will also control adherence to the protocol at the study site. They will arrange for the supply of IMP and ensure appropriate storage conditions are maintained.

Monitoring visits will be conducted according to all applicable regulatory requirements and standards. The Investigator must permit study related monitoring by providing direct access to source data and to the patients' medical histories. The Clinical Monitors will perform monitoring visits at each site at regular intervals during the study and after the study has completed, as appropriate. The monitor will make written reports to the Sponsor on each occasion when contact with the Investigator is made, regardless of whether it is by phone or in person.

Monitoring visits must be conducted according to the applicable ICH-GCP guidelines to ensure protocol adherence, quality of data, study treatment accountability, compliance with regulatory requirements, and continued adequacy of the investigational site and its facilities.

During monitoring visits, entries in the eCRFs will be compared with the original source documents (source data verification). For this study, the data will be 100% checked and verified.

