The monitor will review the eCRFs and evaluate them for completeness and consistency. The eCRF will be compared with the source documents to ensure that there are no discrepancies between critical data. All entries, corrections and alterations are to be made by the responsible Investigator or his/her designee. The monitor cannot enter data in the eCRFs. Once clinical data of the eCRF have been submitted to the central server, corrections to the data fields will be audit trailed, meaning that the reason for change, the name of the person who performed the change, together with time and date will be logged. Roles and rights of the site staff responsible for entering the clinical data into the eCRF will be determined in advance. If additional corrections are needed, the responsible monitor or Data Manager will raise a query in the EDC application. The appropriate study site staff will answer queries sent

to the Investigator. This will be audit trailed by the EDC application meaning that the name of investigational staff, time, and date stamp are captured.

The eCRF is essentially considered a data entry form and should not constitute the original (or source) medical records unless otherwise specified. Source documents are all documents used by the Investigator or hospital that relate to the patient's medical history, that verify the existence of the patient, the inclusion and exclusion criteria, and all records covering the patient's participation in the study. They include laboratory notes, ECG results, memoranda, pharmacy dispensing records, patient files, etc. The eCRFs should be completed by the Investigator or a qualified designee from the site as soon as the data are available. Instructions for the completion of eCRFs will be provided.

The eCRFs will be considered complete when all missing, incorrect and/or inconsistent data have been accounted for. If some assessments are not done, or if certain information is not available or not applicable or unknown, the Investigator should indicate this in the eCRF using appropriate item or form level comments.

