6. GENERAL CONSIDERATIONS

The following descriptive statistics will be presented in summary tables:

- Continuous variables: number (valid cases), mean, median, standard deviation (SD), minimum, and maximum
- Categorical variables: summarized by treatment group using frequency tables (frequencies and percentages). Percentages are routinely based on the total within the group count excluding the

Document:	CCI	Version Number:	1.0
Author:	PPD	Version Date:	06 Oct 2017
Template No:	CCI	Reference:	CCI
Effective Date:	01Apr2016		

missing category if not otherwise mentioned. Missing category with zero count will not be presented.

In general, the number of decimal places displayed for each statistic will be determined as follows:

- Mean and median: 1 more than the number of decimal places allotted in the raw data received from data management.
- SD: 2 more than the number of decimal places allotted in the raw data.
- Minimum and maximum: equal to the number of decimal places allotted in the raw data.
- Percentages: All percentages between 0% and 100% will be rounded to one decimal unless there is a need to report more than one decimal for percentages.
- Ranges will be reported to the same number of decimal places displayed by the laboratory.

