7.3. MISSING DATA

Missing safety and efficacy data will not be imputed. For efficacy data the missing data handling approach will be based on MMRM.

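### SAP 16.1 sets a missing AE severity to Grade 5, the death grade, whatever the recorded outcome, so the severity table can show a fatal-grade event for a survivor

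*SAP*

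**What the plan says.** SAP 16.1 (Adverse Events) gives one sentence for two blank fields: "Missing relationship/missing severity would be considered by the worst case as" Related for relationship and Grade 5 for severity. It does not refer to the outcome or seriousness of the event. The same section plans a CTCAE summary by system organ class and preferred term, a count of patients with a treatment-emergent event of Grade 3 or higher, a row for the number of deaths, and a separate listing of deaths.

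Protocol 8.1.1 grades events by CTCAE 4.03 and gives the top grade as "Grade 5: Death related to AE". It also states: "Death is not considered an AE but an outcome". Protocol 8.1.1.1 asks the investigator to record "severity, action taken, outcome, and relationship to IMP", so grade and outcome are separate items on the eCRF.

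SAP 7.3 gives a different general rule: "Missing safety and efficacy data will not be imputed".

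**The concern.** A worst-case rule is reasonable when the assigned value could be true. An event with no recorded relationship may have been related. An event with no usable dates may have been treatment-emergent, as SAP Appendix 1 assumes. Grade 5 is different: for a patient known to have survived the event, it cannot be true.

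Incidence and severity of adverse events is the primary endpoint (Protocol 4.1), so the error would fall in a primary-endpoint table. Nor is it reliably conservative, because the rule applies to both arms: a blank grade on placebo would put a fatal-grade event in the control column and make ARGX-113 look safer by comparison. If relationship is blank as well, the same sentence produces a drug-related, fatal-grade event.

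The SAP text does not say how the deaths row and deaths listing are derived. If they come from outcome, they will disagree with the severity table. If they were taken from grade, they would count a death that did not happen.

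**Working it through.** The plan states no figure to reproduce. The check is a comparison of provisions, followed by simple proportions.

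**Provisions side by side, for a non-fatal AE with a blank grade**

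| Source | What it gives |
|---|---|
| Protocol 8.1.1.1, eCRF outcome field | Patient did not die of the event |
| SAP 16.1, missing severity | Grade 5 |
| Protocol 8.1.1, meaning of Grade 5 | Death related to the event |
| SAP 7.3, general rule | No imputation of safety data |

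The first and third rows cannot both hold for the same event. The second and fourth rows also conflict. In practice the specific rule in 16.1 would be applied over the general one in 7.3.

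**Can a blank survive to database lock?** Severity is a requested field. Protocol 9.3 says "For this study, the data will be 100% checked and verified", and Protocol 9.4 provides for queries, so blanks should be uncommon. However, Protocol 9.4 also says that if certain "information is not available or not applicable or unknown, the Investigator should indicate this in the eCRF". A blank is therefore not excluded.

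**Size if one blank survives**

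Inputs: 12 patients planned per arm (SAP 7.2), 24 in total; one surviving patient with one ungraded AE; no true Grade 5 events; k patients in that arm already counted with a treatment-emergent event of Grade 3 or higher.

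- Grade 5 row, that arm: 0/12 = 0.0% becomes 1/12 = 8.3%.
- Grade 5 row, overall column if shown: 1/24 = 4.2%.
- Grade 3 or higher row, that arm: k/12 becomes (k+1)/12 if the event is treatment-emergent and the patient has no other such event of Grade 3 or higher. Otherwise it stays k/12.

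**The same record under each handling** (Grade 3 or higher column under the two conditions just given)

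| Handling | Grade 5 | Missing | Grade 3 or higher |
|---|---|---|---|
| SAP 16.1 as written | 1/12 (8.3%) | none | (k+1)/12 |
| Missing row, Grade 5 only if outcome fatal | 0/12 (0.0%) | 1/12 (8.3%) | k/12 |
| Worst case capped at Grade 4 | 0/12 (0.0%) | none | (k+1)/12 |

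**The case against.** The strongest reply is that the rule may never operate. CTCAE grading is the investigator's judgement, and Protocol 8.1.1 supplies general definitions for terms without their own scale, so it is hard to see why a grade would be unknown. The form is reviewed, e-signed and verified against source, and Protocol 9.4 treats an eCRF as complete only once missing items are accounted for. This stands as a limit on likelihood. It does not defend the value chosen for the case the SAP itself provides for.

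Second, nothing says deaths are derived from grade. The protocol calls death an outcome, deaths have their own row and listing, and the mock shells, which may settle the point, are not among the documents. This also stands: the death count need not be wrong. What is established is a possible contradiction between the severity table and the deaths row.

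Third, SAP 16 plans no between-group tests on safety data, so no inference changes. That is true. But this primary endpoint is reported descriptively, so the tables are the result.

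Fourth, a Missing row gives up conservatism, because an ungraded severe event would drop out of the Grade 3 or higher count. A Grade 4 cap keeps that conservatism but still assigns a grade without evidence. This is a real trade-off between the two remedies. Neither of them assigns a value that survival rules out.

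**Conclusion.** The concern holds: the rule is wrong as written, because it assigns the death grade without checking the outcome field. The contradiction is certain from the text. Its effect is conditional on a non-fatal event keeping a blank grade to database lock. Given one such event and 12 patients per arm, the arm's Grade 5 row is overstated by 8.3 percentage points, and the Grade 3 or higher row may gain one patient. The documents give neither an expected number of events nor a rate of blank grades, so no probability is attached. Practical impact is probably small. It should still be fixed, because it concerns the primary endpoint and the cost is trivial. The conflict with SAP 7.3 is secondary and is a matter of harmonising the text.

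**What to change.** In SAP 16.1:

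1. Assign Grade 5 to a missing grade only when the recorded outcome of that event is fatal.
2. Show every other missing grade in a Missing severity row, with the arm's Safety Analysis Set N as denominator. SAP 6 already allows for such a category ("Missing category with zero count will not be presented", so it appears only when needed). Its default percentages leave missing values out of the denominator, however, so the AE tables must state the different one. If a worst-case value is preferred, cap it at Grade 4 and footnote that it still counts in the Grade 3 or higher row.
3. State that the deaths row and deaths listing are derived from the outcome field.
4. Keep Related for a missing relationship.

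In SAP 7.3, name the AE rules in 16.1 and Appendix 1 as exceptions to the no-imputation statement.

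The cost is two or three sentences of SAP text and about one line of derivation code. No new data are needed, since outcome is already on the eCRF. The change belongs before the SAP sign-off that Protocol 10.4 places ahead of unblinding and database lock. Correcting the rule after a spurious Grade 5 had appeared would be a post-hoc change to a primary-endpoint table.
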